#### Medical Assessments

During the screening visit, vital signs, physical exam, and clinical laboratory tests (i.e. CBC with differential, complete metabolic panel (CMP) (including electrolytes, LFTs, BUN, creatinine and glucose), TFTs, urine drug screen, and routine urinalysis) will be completed. A pregnancy test will be given to all females enrolled in the study prior to participating in the study sessions. Only the subject will be told the results of this testing. A total of 30 cc of blood will be drawn at this visit. In addition, an EKG will be performed and read in order to rule out any cardiac abnormalities. If the urine drug screen or the pregnancy test is positive, the subject will not be able to participate in the protocol.

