#### PATIENTS WITH SOCIAL ANXIETY DISORDER:

##### *Inclusion Criteria:*

- 1) Male or female (post-menopausal, surgically sterile, or negative pregnancy test at screening and agreement to utilize an established birth control including complete abstinence during the testing period) between the age of 18 and 65 yrs.
- 2) Meet DSM-5 criteria for social anxiety disorder by structured clinical interview (SCID) and have a LSAS score >60. No current diagnosis of a psychotic disorder.
- 3) Psychiatrically stable. Patients must have had stable doses of all psychiatric medications for the month prior to treatment prior to study enrollment. If a patient has just begun taking an SSRI or SNRI, the patient must be taking the medication for at least 2 months prior to starting the study and it must be at least 1 month since SSRI dose change. Patients cannot receive CBT while in the study.
- 4) Medically and neurologically healthy on the basis of physical examination, CMP (including LFT's), TFT's, CBC w/ diff, urinalysis, urine toxicology, EKG, and medical history. Individuals with stable medical problems that do not have CNS effects or interfere with medications administered (e.g., oral hypoglycemics) may be included if their medications have not been adjusted in the month prior to entry.
- 5) Patients abusing cocaine, opiates, and PCP will be excluded from the study. A urine toxicology screen will be used to ensure these substances are not being abused prior to study enrollment.
- 6) Able to provide written informed consent according to the Yale Human Investigation Committee (HIC) guidelines in English.

**6. Subject classification:** Check off all classifications of subjects that will be specifically recruited for enrollment in the research project. Will subjects who may require additional safeguards or other considerations be enrolled in the study? If so, identify the population of subjects requiring special safeguards and provide a justification for their involvement.

 Children	 Healthy	 Fetal material, placenta, or dead fetus
 Non-English Speaking	 Prisoners	 Economically disadvantaged persons
 Decisionally Impaired	 Employees	 Pregnant women and/or fetuses

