**Exclusion Criteria:**

1. Positive pregnancy test
2. History of substance abuse disorder (cocaine, opiates, PCP) within the last 6 months or positive urine toxicology on screening (within the previous 6 months).
3. History of pervasive developmental disorder or psychotic disorder by DSM-IV-TR criteria
4. Medical comorbidity that significantly increases the risks associated with ketamine infusion (e.g. untreated hypertension, significant cardiovascular disease, glaucoma)

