Participants will be excluded from the study if they present with major active suicidal ideation, a history of serious medical or neurological illness, current psychoactive substance dependence (with the exception of marijuana, caffeine, and nicotine), mental disorders due to identified medical conditions, or non-affective psychotic disorder. Participants will also be excluded if they manifest signs of major medical or neurological illness on examination or as detected by laboratory studies. The routine laboratory studies will include a CMP (including LFT's), TFTs, , CBC w/ diff, urinalysis, urine toxicology, EKG, and medical history, and a urine pregnancy test for females. Care will be taken to exclude pregnant women. Female participants will have a serum pregnancy test prior to receiving any treatment or testing in the study and will be informed of the importance of not becoming pregnant during the study. Participants will be excluded if they are judged to be so clinically unstable that participation in the study might represent a significant clinical risk or are unwilling to stay on a stable medication regimen for the length of this study.

After lab results are received and if the patient remains eligible as indicated by meeting the inclusion criteria, the patient will be called in order to schedule their first infusion. In the case of abnormal test results, the proper referrals will be made to ensure the patients receive the appropriate clinical care.

Eligibility will be **determined by** the PI and co-investigators based on the study inclusion criteria (above).

**9. Risks:** Describe the reasonably foreseeable risks, including risks to subject privacy, discomforts, or inconveniences associated with subjects participating in the research.

**Ketamine administration:** Ketamine is a medication approved by the Food and Drug Administration to be used as an anesthetic. It is a dissociative anesthetic that has been used in humans since the late 1960's. Despite extensive experience there is no clear evidence of long-

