Health Center Investigational Drug Service phone number, and regular hours telephone numbers of their study physician and research support staff ([name] [contact]), should unpleasant effects occur after the subject has left the testing facility. All participants are contacted 1, 2, 3, 5, 7, 10, 14, 21, and 28 days after each infusion for safety reasons. In addition, participants will be contacted 1, 2, 3, 5, 7, 10, and 14 days after each infusion to administer symptom ratings. Participants will be instructed and encouraged to contact the treatment team between scheduled meetings should their distress worsen.

In order to enroll in the study, patients must not have a lifetime history of substance abuse or dependence, thereby reducing the risk of ketamine substance abuse/dependence by study participants.

**Blood drawing/intravenous placement:** The risks of blood draws and intravenous line placements are rare, and when these are done under sterile conditions by trained personnel the occurrence is even more remote.

**Psychiatric evaluation, rating scales, questionnaires, speech tasks, and attention bias tasks:** In order to minimize risks associated with the psychiatric ratings and ensure the accuracy of reporting, these measures will be administered by a trained research nurse and supervised by a study physician. During the impromptu speech, participants have the option to stop the speech at any time if they experience significant distress.

**Clinical deterioration:** If a participant shows significant worsening of symptoms, he or she will be evaluated for clinically appropriate pharmacological and non-pharmacological treatments by a clinic psychiatrist and followed until successful contact with a community provider is made. Patients will be informed that the decision to initiate a course of psychotropic medication will not affect their eligibility to participate in future studies, to receive treatment at the Connecticut Mental Health Center or Yale, or to receive treatment on a private basis from a referring clinician.

**11. Data and Safety Monitoring Plan:** Include an appropriate Data and Safety Monitoring Plan (DSMP) based on the investigator's risk assessment stated below. (Note: the HIC will make the final determination of the risk to subjects.) For more information, see the Instructions, page 24.

- a. What is the investigator's assessment of the overall risk level for subjects participating in this study? This is a moderate risk study.

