f. Who will have access to the protected health information (such as the research sponsor, the investigator, the research staff, all research monitors, FDA, Yale Cancer Center Data and Safety Monitoring Committee (DSMC), SSC, etc.)?(please distinguish between PHI and de-identified data)

In addition to study investigators, members of the HIC, the study sponsor, and the FDA may have access to study data.

g. If appropriate, has a [Certificate of Confidentiality](#) been obtained?

A Certificate of Confidentiality has been obtained to protect the drug toxicology results. Where possible, information will be destroyed that may link the subject to illicit drug use. Since a CMHC chart will need to be created for these subjects by virtue of their visit to the site, there is a concern that these results could be traced back to the subject. Subjects who test positive on the toxicology test will not be able to participate in this protocol. Subjects will be encouraged to seek treatment for their substance use, as appropriate.

h. Are any of the study procedures likely to yield information subject to mandatory reporting requirements? (e.g. HIV testing – reporting of communicable diseases; parent interview - incidents of child abuse, elderly abuse, etc.). Please verify to whom such instances will need to be reported.

Although considered unlikely to be encountered, limits to confidentiality such as mandatory reporting requirements for abuse of children or the elderly will be complied with.

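### The lifetime substance-history bar under Minimizing Risks is absent from the numbered eligibility criteria and leaves the plan's narrower substance-history rules with almost no effect

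*Combined protocol and SAP*

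**What the plan says.** All references are to the combined protocol and SAP. Four places in Section V state a rule about substance history.

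- **Item 5, inclusion criterion 5:** "Patients abusing cocaine, opiates, and PCP will be excluded from the study". A urine screen before enrolment is the stated check.
- **Item 7, exclusion criterion 2:** "History of substance abuse disorder (cocaine, opiates, PCP) within the last 6 months or positive urine toxicology on screening".
- **Item 8, narrative exclusions:** "current psychoactive substance dependence (with the exception of marijuana, caffeine, and nicotine").
- **Item 10, Minimizing Risks:** "patients must not have a lifetime history of substance abuse or dependence, thereby reducing the risk of ketamine substance abuse/dependence by study participants". The sentence is worded as a requirement for enrolment. It lists no substances and gives no exception.

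Item 8 also says how eligibility is settled. After the laboratory results, "if the patient remains eligible as indicated by meeting the inclusion criteria, the patient will be called in order to schedule their first infusion". The decision rests with "the PI and co-investigators based on the study inclusion criteria (above").

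Two further places, Medical Assessments (Section V, item 3) and the Certificate of Confidentiality answer (Section VIII, item g), repeat that a positive drug screen bars participation. They add no history rule.

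**The concern.** The risk section tells the ethics committee that past substance problems are screened out over the whole lifetime, and that this reduces the risk of ketamine abuse. The criteria that the eligibility step points to do not contain that condition. Whether some patients can enrol therefore depends on which paragraph is applied, and compliance cannot be audited against a single rule.

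This bears on safety. Sections V.3 and V.10 put substance abuse or dependence first in their list of the most serious possible side effects of ketamine, and Section VI, A.7 cites abuse potential as a reason not to continue supply. Item 10 is the only place that offers a substance-history rule as mitigation of that risk.

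**Working it through.** There is no figure in the plan to reproduce and no formula applies. The check is a count and a side-by-side reading.

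**Count.** 6 inclusion + 4 exclusion = 10 numbered criteria. Two of the 10 concern substances (inclusion 5, exclusion 2). None of the 10 has a lifetime look-back. Of the four places with a substance-history rule, one (item 10) has it.

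**The rules side by side.**

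| Place in Section V | Substances | Look-back | Exceptions |
|---|---|---|---|
| Inclusion criterion 5 | Cocaine, opiates, PCP | Present abuse | None stated |
| Exclusion criterion 2 | Cocaine, opiates, PCP; or a positive screen | 6 months | None stated |
| Item 8 narrative | Psychoactive substances (dependence) | Current | Marijuana, caffeine, nicotine |
| Item 10 | Not limited (abuse or dependence) | Lifetime | None stated |

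**Test cases, each with a negative urine screen.** Only the substance rules are applied; other criteria could still exclude the patient.

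| Patient | Inclusion 5 | Exclusion 2 | Item 8 | Item 10 |
|---|---|---|---|---|
| Cocaine, opiate or PCP disorder that ended more than 6 months ago | Passes | Passes | Passes | Barred |
| Past alcohol dependence, not current | Passes | Passes | Passes | Barred |
| Current nicotine dependence | Passes | Passes | Exempt | Barred if read literally |

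**What happens if all four are applied together.** Anyone abusing a substance now, with a disorder in the last 6 months, or currently dependent also has a lifetime history. Every patient caught by the three narrower history rules is therefore already caught by item 10. The 6-month window, the limit to current dependence and, on a literal reading, the three exemptions then change nobody's eligibility. The only limb that still works independently is the positive screen, which can catch someone with no history of a disorder.

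**What the eligibility step points to.** Item 8 refers to inclusion criteria placed above it. The lifetime condition comes later, in item 10, and neither sentence on eligibility in item 8 refers to it.

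**The case against.** The strongest reply is that the rules are cumulative. A patient must satisfy all of them, so the strictest holds and nothing is contradictory. That is right as logic, and it is why this is not put as an outright contradiction. It does not explain why the plan sets a three-drug, 6-month window and three exemptions that the stricter rule would empty, and no other text says which history rule governs.

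Three stronger readings are tempting and are not supported.

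- **Staff would not apply the lifetime bar.** This takes the reference to inclusion criteria literally. Read that way, it would also drop all four exclusion criteria, which cannot be meant. Item 7 uses the term just as loosely, answering a question about both kinds of criteria by pointing to the inclusion list. Binding conditions stand outside the lists elsewhere too: fear of public speaking, active suicidal ideation and willingness to keep a stable regimen, all in item 8. The principal investigator, who shares the eligibility decision, is responsible for protocol compliance. The SCID, the clinical interview and the provider contact could reveal a past history. The consent pages are not available for review, and the case report forms were still to be developed.
- **Item 8 expressly admits patients dependent on marijuana, caffeine or nicotine.** It only removes them from its own exclusion. Because item 10 leaves its terms undefined, carrying the exemption across is a reasonable reading.
- **The drug-screen rule is also at fault.** The screening panel is not specified, so nothing can be concluded about marijuana and a positive result.

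What stands is the omission from the numbered criteria and the lack of any statement reconciling the four rules.

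**Conclusion.** The inconsistency is real and should be corrected, at low priority. A condition of enrolment offered as a safeguard appears in 0 of 10 numbered criteria and in 1 of 4 places with a substance-history rule, and it makes the other three almost redundant.

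If the bar were missed at enrolment, the loss of protection would be partial. The narrower history rules and the drug screen remain, infusions are supervised with 3 hours of monitoring, safety contacts run to day 28 after each infusion, ketamine is not continued after the study, and the plan describes the serious side effects as rare. It would be wrong to infer that the lifetime bar is the only protection, since item 10 claims only that it reduces the risk.

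The documents give no prevalence of past substance disorders, so the number affected among the 18 planned patients cannot be estimated. The primary outcome, power and analysis are unaffected. The conclusion rests on reading item 10 as it is worded, as a requirement for enrolment.

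**What to change.** Reconcile inclusion criterion 5, exclusion criterion 2, the item 8 narrative and the item 10 sentence into one numbered substance-history criterion. It should state the substances covered, the look-back period and any exceptions. Have the eligibility step in item 8 and the risk text in item 10 both refer to it. Which rule applies is for the investigators and the ethics committee to decide.

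The cost is a wording amendment with ethics review. Nothing changes in the design or the analysis.

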## **Moderate Risk DSMP**

### **1. Personnel responsible for the safety review and its frequency:**

The principal investigator will be responsible for monitoring the data, assuring protocol compliance, and conducting the safety reviews at the specified frequency which must be conducted at a minimum of every 6 months (including when re-approval of the protocol is sought). During the review process, the principal investigator (monitor) will evaluate whether the study should continue unchanged, require modification/amendment, or close to enrollment. Either the principal investigator or the IRB have the authority to stop or suspend the study or require modifications.

**2. The risks associated with the current study are deemed moderate for the following reasons: (choose those that apply)**

1. We do not view the risks associated with the ketamine infusion as minimal.
2. Given the now established safety and validity of the current dose of ketamine in our prior work, we do not view the proposed studies as high risk.

Although we have assessed the proposed study as one of moderate risk, the potential exists for anticipated and/or unanticipated adverse events, serious or otherwise, to occur since it is not possible to predict with certainty the absolute risk in any given individual or in advance of first-hand experience with the proposed study methods. Therefore, we provide a plan for monitoring the data and safety of the proposed study as follows:

**3. Attribution of Adverse Events:**

Adverse events will be monitored for each subject participating in the study and attributed to the study procedures / design by the principal investigator ([name]) according to the following categories:

- a.) Definite: Adverse event is clearly related to investigational procedures(s)/agent(s).
- b.) Probable: Adverse event is likely related to investigational procedures(s)/agent(s).
- c.) Possible: Adverse event may be related to investigational procedures(s)/agent(s).
- d.) Unlikely: Adverse event is likely not to be related to the investigational procedures(s)/agent(s).
- e.) Unrelated: Adverse event is clearly not related to investigational procedures(s)/agent(s).

**4. Plan for Grading Adverse Events:**

The following scale will be used in grading the severity of adverse events noted during the study:

1. Mild adverse event
2. Moderate adverse event
3. Severe

**5. Plan for Determining Seriousness of Adverse Events:**

**Serious Adverse Events:**

In addition to grading the adverse event, the PI will determine whether the adverse event meets the criteria for a Serious Adverse Event (SAE). An adverse event is considered serious if it:

1. is life-threatening OR
2. results in in-patient hospitalization or prolongation of existing hospitalization OR
3. results in persistent or significant disability or incapacity OR
4. results in a congenital anomaly or birth defect OR
5. results in death OR
6. based upon appropriate medical judgment, may jeopardize the subject's health and may require medical or surgical intervention to prevent one of the other outcomes listed in this definition, OR
7. adversely affects the risk/benefit ratio of the study

An adverse event may be graded as severe but still not meet the criteria for a Serious Adverse Event. Similarly, an adverse event may be graded as moderate but still meet the criteria for an SAE. It is important for the PI to consider the grade of the event as well as its "seriousness" when determining whether reporting to the IRB is necessary.

**6. Plan for reporting Reportable Adverse Events and other unanticipated problems involving risks to subjects or others to the IRB**

The principal investigator will report the following types of events to the IRB: a) adverse events that are serious or life-threatening AND unanticipated (or anticipated but occurring with a greater frequency than expected) AND possibly, probably or definitely related to the drug/device/intervention; and b) other unanticipated problems involving risks to subjects or others.

These adverse events or unanticipated problems involving risks to subjects or others will be reported to the IRB in accordance with IRB Policy 710, using the appropriate forms found on the website.

**7. Plan for reporting adverse events to co-investigators on the study, as appropriate the protocol's research monitor(s), and funding and regulatory agencies, and regulatory and decision-making bodies.**

For the current study, the following individuals, funding, and/or regulatory agencies will be notified (choose those that apply):

All Co-Investigators listed on the protocol.

Food and Drug Administration

The principal investigator ([name]) will conduct a review of all adverse events upon completion of every study subject. The principal investigator will evaluate the frequency

and severity of the adverse events and determine if modifications to the protocol or consent form are required.

- d. For multi-site studies for which the Yale PI serves as the lead investigator: N/A
  - i. How will adverse events and unanticipated problems involving risks to subjects or others be reported, reviewed and managed?
  - ii. What provisions are in place for management of interim results?
  - iii. What will the multi-site process be for protocol modifications?

**12. Statistical Considerations:** Describe the statistical analyses that support the study design.

We will use a paired t-test to compare average improvement over the first 3 days following infusion between ketamine and saline. Ketamine greatly reduces anxiety and depressive symptoms in MDD with an effect size of 1.4-1.5 in similarly designed saline controlled studies (Zarate, Singh et al. 2006). If ketamine proves to be as efficacious in SAD as it is in MDD, a sample size of 18 would allow a placebo to ketamine comparison study to have statistical power greater than 0.80 to detect a statistically significant change at the  $\alpha = 0.05$  level (Cohen 1988). However, it is quite possible that the benefits of ketamine will be smaller in SAD than depression. Therefore, even if the results of our primary analysis are not statistically significant, we would consider having 6 of 18 patients exhibiting a response to ketamine (but not placebo) during the first week following infusion as sufficient evidence towards conducting a more definitive trial. Treatment response is defined as at least a 30% reduction in VAS scores anytime in the first 3 days following infusion.

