### SECTION V: RESEARCH PLAN

#### 1. Statement of Purpose: State the scientific aim(s) of the study, or the hypotheses to be tested.

***To determine the short-term efficacy of ketamine compared to placebo in the treatment of severe social anxiety disorder (SAD).*** We will conduct a crossover trial in which 18 patients with severe SAD will be given a single infusion of ketamine or saline (placebo) and their SAD symptoms will be followed over a two week period. We will require 4 weeks between infusion doses in order to minimize carryover effects. Our primary outcome will be average improvement during the first 3 days following infusion on the Visual Analog Scale (VAS) of Anxiety States.

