**Overview:**

We propose a double-blind, placebo-controlled crossover trial to study the effects of intravenous ketamine for the treatment of SAD. All patients will be offered the option of at least one first line treatment (an SSRI, SNRI, or CBT) prior to study enrollment.

We will perform the first blinded infusion (ketamine or saline) on the first study day. The second blinded infusion (ketamine or saline) will be administered 28 days after the initial infusion. The study investigators will be blinded to the order of infusion which will be determined offsite by the Connecticut Mental Health Center (CMHC) Investigational Drug Service. The infusions will occur on the Clinical Neuroscience Research Unit (CNRU). Patients will be followed with clinical ratings and behavioral assessments for 2 weeks following each infusion. Clinical ratings (excluding the infusion day) will take place at a separate location (the Yale Child Study Center) by a rater unaware of clinical and side-effect ratings on the day of infusion. The side-effects and psychotomimetic ratings for ketamine will be performed by a separate rater, than the ratings of anxiety and depression. We chose this design because the psychometric and physiologic side-effects of ketamine often lead to unblinding and because the beneficial effects of ketamine have lasted for 3 weeks in depression, making the carry-over effects in shorter-duration crossover studies problematic.

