Ketalar is chemically designated *d,l* – 2- (0-chlorophenyl)-2-(methylamino) cyclohexanone hydrochloride. It is formulated as a slightly acidic (pH 3.5-5.5) sterile solution for intravenous or intramuscular injection in concentrations containing the equivalent of either 10, 50, or 100 mg ketamine base per milliliter and contains not more than 0.1 mg/mL Phemerol® (benzethonium chloride) added as a preservative. The 10mg/mL solution has been made isotonic with sodium chloride. The medication will be obtained and stored at the CMHC research pharmacy, and will be picked up by investigators on the morning of infusion.

Check applicable Investigational Drug Service utilized:

YNHH IDS  
 CMHC Pharmacy  
 PET Center

Yale Cancer Center  
 West Haven VA  
 None

Other:

*Note: If the YNHH IDS (or comparable service at CMHC or WHVA) will not be utilized, explain in detail how the PI will oversee these aspects of drug accountability, storage, and preparation.*

**5. Use of Placebo:**  Not applicable to this research project

If use of a placebo is planned, provide a justification which addresses the following:

a. Describe the safety and efficacy of other available therapies. If there are no other available therapies, state this.

Since this is a crossover trial, all subjects will receive both ketamine and placebo during the course of the study. A placebo control is necessary because there is a significant improvement with time and to treatment expectancy that occurs in anxiety disorders. Using a crossover design allows all subjects to get the research medication being studied in the protocol, yet provide an appropriate comparison condition.

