Before beginning the study, participants will be informed of typical first-line treatments for SAD. Generally, one would try all three first line treatments sequentially followed by an MAOI as standard of care treatment(Pilling, Mayo-Wilson et al. 2013). However, roughly one-third to one-half of patients with generalized SAD do not experience significant clinical benefit from the combination of first-line interventions such as pharmacotherapy with selective serotonin reuptake inhibitors (SSRI), venlafaxine, or cognitive behavioral therapy (CBT) (Blomhoff, Spetalen et al. 2001, Davidson 2004, Baldwin, Anderson et al. 2005). Benzodiazepines, gabapentin, pregabalin, and monoamine oxidase inhibitors phenelzine and moclobemide are also effective in the treatment of social anxiety; however, to our knowledge, there are no randomized, placebo-controlled studies that examine the treatment of SAD patients who do not respond to first-line treatments. Moreover, aside from benzodiazepines, which have significant abuse potential, the medications often take at least a week for the patient to experience

benefits. This delay in anxiolytic effect coupled with side effects, which often begin immediately, can lead to premature discontinuation of these treatments. Finally, there is little evidence that combination of interventions (pharmacologic or psychotherapeutic) is effective(Blanco, Bragdon et al. 2013) (Blomhoff, Spetalen et al. 2001, Baldwin, Anderson et al. 2005).

b. State the maximum total length of time a participant may receive placebo while on the study.

One dose of IV saline will be given, and the patient will not receive the ketamine infusion one month (psychotropic medication changes are not allowed for the duration of the study – two months).

c. Address the greatest potential harm that may come to a participant as a result of receiving placebo.

Anxiety symptoms may not improve or even worsen depending on the clinical course of illness. Subjects have the option of withdrawing from the research protocol at any point if their symptoms worsen. Additionally, inpatient hospitalization resources are available to the investigator if subject's symptoms worsen to the point of requiring inpatient hospitalization as part of the protocol.

d. Describe the procedures that are in place to safeguard participants receiving placebo.

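### The primary paired t-test has no period term and no balance of infusion order is stated; this costs power at modest effects and can shift the estimate if the sequences are unequal

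*Combined protocol and SAP*

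**What the plan says.** The primary analysis is one sentence in Section V, item 12: "We will use a paired t-test to compare average improvement over the first 3 days following infusion between ketamine and saline". The outcome, from the Statement of Purpose (Section V, item 1), is "average improvement during the first 3 days following infusion on the Visual Analog Scale (VAS) of Anxiety States". Neither place names the baseline reading, and Table 1 schedules the VAS both at screening and before each infusion.

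Item 12 claims that "a sample size of 18 would allow a placebo to ketamine comparison study to have statistical power greater than 0.80" at an effect size of 1.4 to 1.5, and then concedes that "it is quite possible that the benefits of ketamine will be smaller in SAD than depression".

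The study is described as randomized. On allocation, the Overview in Section V, item 3 says only that investigators are blinded to the "order of infusion which will be determined offsite by the Connecticut Mental Health Center (CMHC) Investigational Drug Service". No sequence ratio, blocking or other balance is given, and the text contains no period or sequence term.

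The justification for placebo (Section VI.A, item 5) is that "there is a significant improvement with time and to treatment expectancy that occurs in anxiety disorders". The same item says: "Subjects have the option of withdrawing from the research protocol at any point if their symptoms worsen".

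**The concern.** A paired t-test of ketamine minus saline pools patients who had ketamine first with patients who had it second. Suppose improvement after the first infusion differs from improvement after the second by π for reasons unrelated to drug. The paired difference then moves by +π in ketamine-first patients and by −π in saline-first patients.

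- With equal sequences the two movements cancel in the mean but stay in the variance. The estimate is unbiased, and the test is conservative and less powerful.
- With unequal sequences, by chance or after withdrawals, part of π also enters the estimate, in either direction.

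Improvement with time and from expectancy makes such a difference plausible, but the plan does not establish it. The choice of baseline also matters. A single screening VAS cancels from the paired difference and leaves any drift in level over the 28 days in the comparison. A separate pre-infusion VAS for each period removes that drift and leaves only a period difference in the 3-day improvement.

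At stake is whether the trial misses a moderate benefit that the same 18 patients could have shown, and whether an uneven split moves its estimate.

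**Working it through.** **Inputs.** From the plan: n = 18, α = 0.05 (taken as two-sided), effect 1.4 (read as mean over SD of the paired difference). Assumed, because the plan gives no values: effects of 0.50 and 0.70, period differences π from 0 to 0.75, and, where stated, coin-flip order. All are in units of the SD of the paired difference.

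**1. The plan's own figure.** The noncentrality is δ√18 on 17 df. At δ = 1.4 this is 1.4 × 4.243 = 5.94 and power is 0.9999, so the claim of more than 0.80 holds. At δ = 0.70 it is 2.97 and power is 79.9%. At δ = 0.50 it is 2.12 and power is 52%. About 0.70 is therefore the smallest effect with 80% power.

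**2. Paired test under a period difference.** Let D = δ + sπ + e, with s = +1 for ketamine-first, s = −1 for saline-first and SD(e) = 1. Let n1 be the number ketamine-first and n2 the number saline-first.

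- Shift of the estimate: π(n1 − n2)/n.
- Expected sample variance at 9:9: 1 + π² × 18/17. At π = 0.5 this is 1.265 (SD 1.125). At π = 0.75 it is 1.596 (SD 1.263).
- Confidence-interval width relative to the adjusted analysis: SD × t(17)/t(16) = SD × 2.110/2.120. This gives 1.12 and 1.26, so the intervals are 12% and 26% wider.

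**3. Period-adjusted test.** Take each patient's Period 1 minus Period 2 difference and compare the two sequences. Half the difference in sequence means estimates δ, and π cancels. The standard error is ½√(1/n1 + 1/n2) on 16 df.

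- 9:9: 0.236; at δ = 0.70 the noncentrality is 2.97 and power is 79.6%.
- 12:6: 0.25; at δ = 0.70 the noncentrality is 2.80 and power is 74.8%.

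These do not depend on π.

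**4. Power at 9:9 (simulation, at least 100,000 trials per cell), paired vs adjusted.**

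| π | effect 0.70 | effect 0.50 | paired type I error |
|---|---|---|---|
| 0 | 80% vs 80% | 52% vs 51% | 5% |
| 0.25 | 78% vs 80% | 49% vs 51% | – |
| 0.5 | 72% vs 80% | 42% vs 51% | 3% |
| 0.75 | 62% vs 80% | 32% vs 51% | 1.5% |

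At effect 1.4 with 9:9, paired power stays at or above 99.8% for π up to 0.75.

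**5. Unequal sequences, π = 0.5.** At 12 ketamine-first and 6 saline-first the shift is 0.5 × 6/18 = +0.17; at 6:12 it is −0.17. At effect 0.70 the paired test has 90% and 48% power respectively, against 75% adjusted. Its type I error, given either split, is 7%. At 9:6, after three withdrawals from one sequence, the shift is 0.5 × 3/15 = 0.10. Under coin-flip order, Binomial(18, 0.5) gives 24% for 12:6 or worse and 19% for exactly 9:9.

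**6. Averaged over coin-flip order.** Bias is 0 and type I error is 5.0% to 5.1%. Power at effect 0.70, paired vs adjusted, is 80% vs 77% at π = 0, 77.5% vs 77.1% at 0.25, 71% vs 77% at 0.5 and 61% vs 77% at 0.75.

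**The case against.** The case for leaving the test alone has five parts.

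- **Evidence.** The remark on time and expectancy justifies having a placebo. Improvement that is similar after both infusions cancels in the paired difference, and nothing in the documents says that it differs. This stands: the period effect is plausible, not shown.
- **Baseline.** If improvement is read from each pre-infusion VAS, which is a natural reading, drift in level drops out, and differences of 0.5 to 0.75 have no documentary support. This also stands as a limit on size. It does not exclude a period difference in the 3-day response.
- **Break-even.** Without blocking, the paired test is as good or slightly better up to a period difference of about 0.25 to 0.3. This is correct, and it is the reason to adopt blocking and the period term together. At 9:9 the adjustment costs only 0.3 points when there is no period effect.
- **Imbalance.** Silence about allocation is not evidence of imbalance, no withdrawal rate is given, and the 9:6 example needs all three losses in one sequence. Randomization also makes the test valid on average. All true, but the trial will be run with one split, and its estimate carries that split's shift.
- **Consequence.** This is called a pilot study, and 6 of 18 patients responding to ketamine but not placebo would support a further trial even without significance. That softens the cost of a missed result. It is a responder count, however, and does not give a period-adjusted estimate.

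**Conclusion.** The concern holds as a recommended, inexpensive improvement; it is not an error in the stated sample size. The omissions are certain: no period term, and no stated balance of order. Their cost depends on assumed values. With a period difference of 0.5 to 0.75 SD and 9:9 order, the paired test gives up about 8 to 18 points of power at effect 0.70 and about 9 to 19 points at effect 0.50. A 12:6 or 6:12 split with a difference of 0.5 moves the estimate by 0.17 SD. With a difference of 0.25 or less the gain from adjusting is about 2 points at 9:9, and there is essentially none without blocking. The undefined baseline is missing detail that affects how large a period effect could be; it adds no separate weight. Confidence is medium, because the documents give neither the size of a period effect nor the allocation method.

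**What to change.** 1. Have the drug service allocate order from a permuted-block list giving 9:9, for example three blocks of six, with block size concealed from investigators and raters.
2. Make the period-adjusted crossover analysis primary. For each patient take the Period 1 minus Period 2 difference in mean Day 1–3 VAS improvement, and compare these differences between sequences with a two-sample t-test. Report half the difference in sequence means with its 95% confidence interval on n − 2 df. A linear mixed model with treatment, period, sequence and a random patient effect gives the same estimate in patients with both periods.
3. Keep the plain paired t-test as a sensitivity analysis.
4. State which VAS reading improvement is measured from. Any baseline-covariate adjustment should be a sensitivity analysis only, because the Day 28 pre-infusion reading follows the first treatment and may carry its effect.

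The cost is wording in the analysis section, an instruction to the pharmacy and one degree of freedom; no new data are needed. If there is no period effect, the loss at effect 0.70 is about 0.3 points of power at 9:9 and about 5 points if the split ends at 12:6. Items 1 and 2 should therefore be adopted together.
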